9.7.4. Relative Administration Intensity

RAI will be calculated as the cumulative frequency of administration received over the expected number of administrations (see Table 4 and Table 5).

$$RAI = \frac{No.\ of\ administrations\ received}{No.\ of\ expected\ administrations\ during\ the\ time\ period}$$

Treatment exposure outcomes will be assessed across the different maintenance and step-up period. Patients will be censored at the earliest of death, next treatment (CAR-T, BsABs, bendamustine or belantamab), the end of part A or B continuous closed-claim coverage, or the end of data.

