2	Average time between elranatamab or teclistamab claims	Sum of the days between claims for the index drug (continuous) divided by the total number of administrations -1	Index date to the end of follow-up Step-Up Dosing Period

	1	T	T
			Maintenance Periods
2	Frequency of elranatamab or	Total number of inpatient, non-IP, and pharmacy claims of the index drug during the	Index date to the end of follow-up
	teclistamab claims	time period based on vial size (continuous)	Step-Up Dosing Period
			Maintenance Periods
2	Relative Administration Intensity (RAI)	The ratio of the actual administrations received divided by the expected number of administrations according to the US label	Index date to the end of follow-up
		(continuous)	Step-Up Dosing Period
			Maintenance Periods
2	Time to Discontinuation (TTD)	Time in months from first administration until last administration prior to treatment discontinuation (continuous). Treatment discontinuation is defined as an 8-week gap in elranatamab or teclistamab therapy, next treatment after index treatment (CAR-T, BsABs, bendamustine or belantamab), or death.	Index date to the end of follow-up
2	Reason for Discontinuation	Reason for treatment discontinuation used to estimate time to discontinuation, either an 8-week gap in elranatamab or teclistamab therapy, next treatment after index treatment (CAR-T, BsABs, bendamustine or belantamab), or death.	Index date to the end of follow-up
Health care	resource utilization an	d costs	
3	All-cause IP visits	Medical claim for IP (non-emergency department [ED]) visit (dichotomous)	Start of data to 1 day before index date, index date until last recorded dose, and time from discontinuation through time of censoring
		Number of IP (non-ED) visits (continuous)	
3	All-cause OP visits	Medical claim for non-IP/non-ED visit (dichotomous)	Start of data to 1 day before index date, index date until last recorded dose, and time from
		Number of non-IP/non-ED visits (continuous)	discontinuation through time of censoring

3	All-cause ED visits	Medical claim for ED visit (dichotomous) Number of ED visits (continuous)	Start of data to 1 day before index date, index date until last recorded dose, and time from discontinuation through time of censoring
3	All-cause pharmacy claims	Pharmacy claim (dichotomous) Number of pharmacy claims (continuous)	Start of data to 1 day before index date, index date until last recorded dose, and time from discontinuation through time of censoring

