9.7.2. Treatment Exposure Outcomes

Treatment exposure outcomes include RAI and time between administrations. The assessment periods shown in Table 4 are based on the elranatamab label instructions and will be used to measure treatment and dosing-related outcomes for patients receiving elranatamab.¹⁹ The assessment periods shown in Table 5 are based on the teclistamab label instructions and will be used to measure treatment and dosing-related outcomes for patients receiving teclistamab.²⁰ These periods are also provided in Figure 2.

Table 4. Dosing Schedule and Expected Administrations and Vial Size of Elranatamab

Dosing Schedule	Dosing Schedule Time Period		Vial Size
Step-Up	Index date - Day 8	3	44mg/1.1mL, 76mg/1.9mL
Maintenance Period 1	Day 9 - Day 168	1 per week	76mg/1.9mL

[figure not shown]
Maintenance Period 2	Day 169 - Censor	1 every two weeks	76mg/1.9mL
----------------------	------------------	-------------------	------------

Table 5. Dosing Schedule and Expected Administrations and Vial Size of Teclistamab

[figure not shown]
Dosing Schedule	Time Period	Expected Administrations	Vial Size
Step-Up	Index date - Day 7	3	30 mg/3mL
Maintenance Period	Day 8 - Censor	1 per week	153 mg/1.7mL

Figure 2. Dosing Schedule for Elranatamab and Teclistamab

Elranatamab label instructions

Teclistamab label instructions

Dosing outcomes (reported vial size, average time between claims, and frequency of claims) will be assessed during the above time periods regardless of whether the number of administrations during the period matches the number indicated on the label instructions.

Patients will be censored at the earliest of death, next treatment (CAR-T, BsAbs, bendamustine or belantamab), the end of part A or B continuous closed-claim coverage, or the end of data.

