9.7.5. Time to Discontinuation

Prior to the assessment of this outcome, the average follow-up time will be assessed; if the study team deems that the follow-up time is adequate, then TTD will be assessed. TTD is the total amount of time from the index date until the date of discontinuation; treatment discontinuation is defined as an 8-week gap in elranatamab or teclistamab, next treatment after index treatment (CAR-T, BsABs, bendamustine or belantamab), or death. TTD will be assessed as the time in months (1 month = 30.4375 days) using Kaplan-Meier methods. Median time-to-event will be reported along with the IQR. The 95% confidence intervals (CI) for the median time-to-event will be calculated using log-log transformation. Results will be depicted graphically by Kaplan-Meier curves. Patients who do not have a recorded discontinuation event or death will be censored on the earliest of the end of continuous closed-claim coverage or end of data. The percentage of patients who reached the outcome, as well as the percentage of censored patients, will be reported.

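### RAI mixes persistence into administration intensity, because expected administrations keep accruing after a patient stops by the 8-week-gap rule

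*Protocol*

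**What the plan says.** RAI is an Objective 2 variable, and Objective 2 is primary. Table 3 defines it as "The ratio of the actual administrations received divided by the expected number of administrations according to the US label". Section 9.7.4 agrees: "RAI will be calculated as the cumulative frequency of administration received over the expected number of administrations", with the expected counts taken from Tables 4 and 5.

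For elranatamab, Table 4 expects 3 administrations in step-up ("Index date - Day 8"), one per week from Day 9 to Day 168, and one every two weeks in the period "Day 169 - Censor". For teclistamab, Table 5 expects 3 administrations to Day 7 and one per week from Day 8 until censoring.

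The censoring rule in 9.7.2 and 9.7.4 reads "Patients will be censored at the earliest of death, next treatment (CAR-T, BsABs, bendamustine or belantamab), the end of part A or B". The same sentence goes on to specify that this means loss of unbroken closed-claim enrolment, and it adds one last reason, that the data run out.

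Section 9.7.5 gives a wider definition of stopping: "treatment discontinuation is defined as an 8-week gap in elranatamab or teclistamab, next treatment after index treatment (CAR-T, BsABs, bendamustine or belantamab), or death".

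**The concern.** A measure called administration intensity should show how closely dosing followed the label while the patient was being treated. Here the denominator runs on past the point at which the protocol itself classes some patients as discontinued. A low RAI could then mean skipped or delayed doses, early stopping, or long observation after stopping, and the reader could not tell which.

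The protocol recognises the time in question. Section 9.7.3 uses the same censoring rule and sets up a separate resource-use period running from discontinuation to censoring. Section 9.7.6 ties its safety windows to the last administration. The average time between claims in Table 3 stops at the last claim by construction. A patient who took every dose on time and then stopped would show perfect intervals in one Objective 2 result and a low RAI in the next.

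**Working it through.** **Discontinuation routes (9.7.5) against the RAI censoring list (9.7.4)**

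| Route | Ends the RAI denominator? |
|---|---|
| 8-week gap | No |
| Listed next treatment | Yes, at the switch |
| Death | Yes, at death |

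Only the gap is missing. In the other two routes, expected doses still accrue between the last administration and the event. A move to a therapy outside the list, such as a PI or IMiD, does not censor either. Nothing in the protocol confines the RAI denominator to time on treatment.

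**Expected administrations to day T (Tables 4 and 5)**

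- Elranatamab, T above 8: E(T) = 3 + (min(T, 168) − 8)/7 + max(T − 168, 0)/14
- Teclistamab, T above 7: E(T) = 3 + (T − 7)/7

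The protocol states no RAI value to reproduce. The stop and censoring days below are assumptions. The patient receives every expected dose until the stop, so on-treatment intensity is 1.00.

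| Stop day, censoring day | Elranatamab | Teclistamab |
|---|---|---|
| 60, 365 | 10.4/39.9 = 0.26 | 10.6/54.1 = 0.20 |
| 90, 365 | 14.7/39.9 = 0.37 | 14.9/54.1 = 0.27 |
| 90, 540 | 14.7/52.4 = 0.28 | 14.9/79.1 = 0.19 |

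**Check by counting doses on a calendar.** Elranatamab, last dose Day 85, 14 doses received:

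- censored at Day 365: 14/40 = 0.35
- censored at Day 540: 14/52 = 0.27
- denominator ended 56 days after the last dose: 14/22 = 0.64
- denominator ended at the last dose: 14/14 = 1.00

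The 0.64 also shows the lag effect when death or a listed switch comes 56 days after the last dose. By period, with censoring at Day 365, Maintenance Period 1 gives 11/22 = 0.50. Maintenance Period 2 gives 0/15 = 0 if the patient is counted there.

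**What RAI then measures.** Let q be on-treatment intensity, L the stop day and C the censoring day. Then RAI = q × E(L)/E(C). With L = 85 and C = 365 on the dose calendar, E(L)/E(C) = 14/40 = 0.35, so q of 1.0, 0.8 and 0.6 gives 0.35, 0.28 and 0.21. The value still responds to q but is scaled by persistence and by length of observation.

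**The case against.** The strongest defence is that the protocol is consistent about RAI. Table 3, 9.7.2 and 9.7.4 all describe doses delivered against label-expected doses over observed follow-up, and Objective 2 covers interruption and discontinuation. RAI is descriptive and no hypothesis test rests on it. That is fair as to consistency. It does not rescue the label: a ratio that falls because a stopped patient is watched for longer is not intensity.

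A reader might infer several stronger things that the documents do not support.

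- *RAI measures persistence instead of intensity.* It does not; it is the product of the two.
- *RAI will fall at every data cut.* This holds only for gap-discontinuers who remain observed. A patient on treatment and on schedule stays near 1. Section 9.2.1 admits patients up to the latest available data (9.2 says March 2025), so new entrants could offset the decline.
- *The cohorts will differ because their follow-up differs.* No follow-up difference is documented, and 9.7 plans no formal comparison. The two schedules do give different values for the same stop and censoring days.
- *Patients score 0 in periods they never reached on treatment.* This follows only if they are counted there. Section 9.7.4 does not say who contributes to each period.
- *The two descriptions of TTD contradict each other by up to 56 days (56/30.4375 = 1.84 months).* Table 3 ends TTD at the last administration before discontinuation; 9.7.5 says "TTD is the total amount of time from the index date until the date of discontinuation" without dating a gap stop. The two can be read together, so 1.84 months is the spread between possible readings.

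**Conclusion.** The point holds. Followed as written, 9.7.2, 9.7.4 and Tables 4 and 5 keep adding expected administrations after an 8-week-gap stop, and to a lesser extent between the last dose and a later death or listed switch. The effect on an individual patient can be large: 0.37 or 0.27 against an on-treatment 1.00 in the day-90, day-365 illustration. Those days and full adherence before the stop are assumptions.

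No cohort-level size can be derived, because the documents give neither the share of patients who stop by gap nor their subsequent observation time. The short step-up window is little affected. Maintenance Period 1 is affected for anyone who stops before Day 168 and remains observed, even though its end is a fixed day. The defect concerns the interpretation of a primary-objective variable and can be repaired without new data.

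**What to change.** 1. In 9.7.2, 9.7.4 and Tables 4 and 5, compute RAI over time on treatment. End both numerator and denominator at the last administration before discontinuation, or at censoring if the patient has not discontinued.
2. State how doses given after a gap of 8 weeks or more are handled. If only the denominator were cut, a patient who restarts could exceed 1.
3. Count a patient in a maintenance period only if still on treatment when it starts.
4. State in 9.7.5 that the discontinuation date is the last administration, as in Table 3, and use that date for RAI, TTD and the HCRU periods.
5. If the censor-based ratio is kept, report it under another name.
6. Always report the percentage discontinued. Under 9.7.5, TTD is assessed only if the study team judges follow-up adequate, so persistence might otherwise go unreported.

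The cost is protocol wording and a changed denominator. RAI becomes conditional on being on treatment. One asymmetry remains and should be noted: missed doses in a gap shorter than 8 weeks at censoring still count against a patient not yet classed as stopped, while doses falling after a stopper's last administration do not.

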9.7.5. Time to Discontinuation

Prior to the assessment of this outcome, the average follow-up time will be assessed; if the study team deems that the follow-up time is adequate, then TTD will be assessed. TTD is the total amount of time from the index date until the date of discontinuation; treatment discontinuation is defined as an 8-week gap in elranatamab or teclistamab, next treatment after index treatment (CAR-T, BsABs, bendamustine or belantamab), or death. TTD will be assessed as the time in months (1 month = 30.4375 days) using Kaplan-Meier methods. Median time-to-event will be reported along with the IQR. The 95% confidence intervals (CI) for the median time-to-event will be calculated using log-log transformation. Results will be depicted graphically by Kaplan-Meier curves. Patients who do not have a recorded discontinuation event or death will be censored on the earliest of the end of continuous closed-claim coverage or end of data. The percentage of patients who reached the outcome, as well as the percentage of censored patients, will be reported.

9.7.6. Tolerability

The prevalence and incidence for each adverse event (Table 3) will be estimated. All prevalence and incidence estimates will be reported as a percent with corresponding 95% CIs.

Prevalance =
$$(\frac{No.\ of\ patients\ with\ an\ event}{Total\ number\ of\ patients\ in\ the\ cohort})\ x\ 100$$

For the incidence analysis, only patients who did not have the event prior to their index date will be included. The length of the washout is dependent on the outcome (see Table 3).

$$Incidence = \left(\frac{\text{No. of patients with an event that did not have an event in baseline}}{\text{Total number of patients in the cohort}}\right) x \ 100$$

PFIZER CONFIDENTIAL

Patients will be assessed over two time periods: from the index date until 14 days or 90 days after their last administration of the index medication.

Additionally, the time to infection onset will be assessed using unadjusted Kaplan-Meier methods. The median time to event in days will be reported along with the IQR. The 95% CIs for the median time to event will be calculated using log-log transformation.

Patients will be censored at the earliest of death, next treatment (CAR-T, BsABs, bendamustine or belantamab), the end of part A or B continuous closed-claim coverage, or the end of data.

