Exploratory Obj 1	Other infectious hepatitis ²	Medical claim with an ICD-10 code in the inpatient, non-IP or pharmacy setting for infectious hepatitis (other than hepatitis B or C) (dichotomous)	Index date to end of follow-up, where follow-up will be based on last dose of elranatamab or teclistamab (e.g., 14 days after last recorded dose or 90 days after last recorded dose).
Exploratory Obj 1	Helicobacter pylori ²	Medical claim with an ICD-10 code in the inpatient, non-IP or pharmacy setting for helicobacter pylori (dichotomous)	Index date to end of follow-up, where follow-up will be based on last dose of elranatamab or teclistamab (e.g., 14 days after last recorded dose or 90 days after last recorded dose).

Exploratory Obj 1	Candida esophagitis ²	Medical claim with an ICD-10 code in the inpatient, non-IP or pharmacy setting for candida esophagitis (dichotomous)	Index date to end of follow-up, where follow-up will be based on last dose of elranatamab or teclistamab (e.g., 14 days after last recorded dose or 90 days after last recorded dose).				
Exploratory Obj 1	Urinary tract infection ²	Medical claim with an ICD-10 code in the inpatient, non-IP or pharmacy setting for a urinary tract infection (dichotomous)	Index date to end of follow-up, where follow-up will be based on last dose of elranatamab or teclistamab (e.g., 14 days after last recorded dose or 90 days after last recorded dose).				
Exploratory Obj 1	Time to infection onset	Time in days from index date to first infection for the following infections:	Index date until censor				
Effectiveness	Effectiveness						
Exploratory Obj 2	os	Time (in months) from index date until date of death (continuous)	Index date until censor				
Exploratory Obj 2	TTNT/D	Time (in months) from index date until the date of the next treatment (CAR-T, BsABs, bendamustine or belantamab) or death (continuous)	Index date until censor				

- 1. Variable will be measured as incident and prevalent. Incident cases have 30-day washout period applied
- 2. Variable will be measured as incident and prevalent. Incident cases have 60-day washout period applied
- 3. Variable will be measured as incident and prevalent. Incident cases have 14-day washout period applied

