9.5. Study Size

As of August 2024, the dataset included 133 patients with a claim for elranatamab. To further assess whether sufficient sample size is available to proceed with the study, power analysis will be completed to assess estimates of precision for a one sample means considering either the elranatamab or teclistamab samples.

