9.7. Data Analysis

This study will be largely descriptive in nature, and no formal statistical comparisons will be performed between groups. All characteristics and outcomes will be reported separately for each cohort. The number of patients who meet study eligibility criteria will be summarized in an attrition table. Inclusion and exclusion criteria will be listed hierarchically and the number of patients remaining at each step will be reported. Patient and treatment characteristics will be summarized using descriptive statistics. Categorical variables will be summarized by the number of available observations, frequency, percentage, and 95% confidence limits. Continuous variables will be summarized by the number of available observations, mean, standard deviation, 95% confidence limits, median, quartiles, minimum, and maximum, where appropriate. The prevalence and incidence, as well as the associated 95% confidence intervals (CI) for each adverse event, will be estimated. Kaplan-Meier methods will be used to estimate the median time to event, including 95% CIs for TTNT/D and OS. All-cause HCRU and MM-related HCRU will be measured as the mean, SD, median, IQR, minimum, and maximum of the total number of IP, OP, ED, and pharmacy claims. Given the variable follow-up time available for each patient, HCRU and costs will be reported, for instance, on a per-patient-per-month (PPPM) basis. Relative Administration Intensity (RAI) will be calculated as the ratio of the actual number of administrations during each time period divided by the expected number of administrations based on the label for the treatment.

Based on the study cohorts of interest, patients may be characterized by the following attributes of interest:

- Demographic characteristics such as age, sex, race/ethnicity, state, and region
- Reason for Medicare enrollment
- Social determinants of health such as household income, education level, marital status, and home ownership

PFIZER CONFIDENTIAL

- Clinical characteristics such as comorbidity and past treatment status
- Healthcare resource utilization such as hospitalization and place of service distribution

Subgroup analysis will identify samples of patients based on reason for Medicare entitlement: disabled beneficiaries, beneficiaries with end-stage renal disease (ESRD), and beneficiaries aged 65 to 115 years qualifying by age.

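### The incidence formula in section 9.7.6 divides by the whole drug cohort, although patients with the event before index are excluded from the incidence analysis

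*Protocol*

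**What the plan says.** Section 9.7.6 of the protocol plans a prevalence and an incidence, each as a percentage with a 95% CI, for every adverse event in Table 3.

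- Population for incidence: "For the incidence analysis, only patients who did not have the event prior to their index date will be included".
- Numerator for incidence: "No. of patients with an event that did not have an event in baseline".
- Denominator: the prevalence formula divides by "Total\ number\ of\ patients\ in\ the\ cohort", and the incidence formula repeats the same words.
- Washout: section 9.7.6 says that its length depends on the outcome and refers to Table 3. The table's footnotes set three lengths: "Incident cases have 30-day washout period applied", "Incident cases have 60-day washout period applied" and "Incident cases have 14-day washout period applied".
- Meaning of cohort: section 9.7 says "All characteristics and outcomes will be reported separately for each cohort", where the cohorts are the elranatamab and teclistamab groups.

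The protocol does not define an event-specific at-risk denominator anywhere. Section 9.8 commits the analysts to follow the protocol strictly.

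**The concern.** The population sentence and the formula describe different quantities. The sentence describes a risk among patients who could have a new event. The formula counts new events among those patients but spreads them over everyone, including patients barred from the numerator.

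The result mixes two things: how often the event starts after index, and how common it already was before index. The more common an event is in the washout, the lower its reported incidence, whatever happens on treatment. The error runs one way, making new-onset events look rarer.

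B need not be negligible. In Annex 2 the renal failure list includes chronic kidney disease and dialysis-status codes, the peripheral neuropathy list includes diabetic neuropathy codes, and the anemia list is broad. Because B/N can differ by event and between the two drug groups, incidences from this formula would not be on a common footing across events or when the two cohorts are read side by side.

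**Working it through.** **Inputs**

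- N: patients in the drug cohort. For illustration N = 133, from section 9.5 ("As of August 2024, the dataset included 133 patients with a claim for elranatamab"). This count precedes the eligibility criteria and the extension of the data to December 2025, so it is not the analysis n.
- B: cohort patients with the event in the washout. The protocol does not give it, so B/N is an assumed range.
- x: patients with the event after index and none in the washout.
- Risk among at-risk patients: assumed. Two values are used: 40%, and 48.8%, the anemia figure that section 7 cites from the phase 2 elranatamab trial.

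The protocol states no incidence value, so there is no figure of its own to reproduce.

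**Algebra**

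- Formula as written: x / N.
- Incidence in the population that the text includes: x / (N − B).
- Ratio of the first to the second: (N − B) / N = 1 − B/N.

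The relative understatement is therefore exactly B/N, and zero when B = 0.

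**Illustration 1: at-risk incidence of 40%**

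- B/N = 10%: 0.40 × 0.90 = 36%
- B/N = 30%: 0.40 × 0.70 = 28%
- B/N = 50%: 0.40 × 0.50 = 20%

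**Illustration 2: N = 133, at-risk risk about 48.8%, whole patients, Wilson 95% CI**

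| B/N | B | N − B | x | As written, x/133 | On patients at risk, x/(N − B) |
|---|---|---|---|---|---|
| 0% | 0 | 133 | 65 | 48.9% (40.5–57.3) | 48.9% (40.5–57.3) |
| 10% | 13 | 120 | 59 | 44.4% (36.2–52.8) | 49.2% (40.4–58.0) |
| 30% | 40 | 93 | 45 | 33.8% (26.3–42.2) | 48.4% (38.5–58.4) |
| 50% | 66 | 67 | 33 | 24.8% (18.2–32.8) | 49.3% (37.7–60.9) |

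At B/N = 50% the two intervals do not overlap.

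**Width of the interval**

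In Illustration 2 the interval as written is narrower whenever B > 0. That does not hold generally. With N = 133, at-risk incidence 80% and B/N = 10%, the Wald half-widths are:

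- as written, p = 0.80 × 0.90 = 0.72: 1.96 × √(0.72 × 0.28 / 133) = 7.6 points;
- on patients at risk, n = 0.90 × 133 = 119.7: 1.96 × √(0.80 × 0.20 / 119.7) = 7.2 points.

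Here the written interval is the wider one. What holds whenever B > 0 and x > 0 is that the interval is centred too low and uses the wrong n.

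**The case against.** **Cohort may mean the at-risk subset.** The restriction stands just before the formula, so an analyst might apply it first and divide by whoever remains. Section 9.4 also uses the word cohort more loosely when it describes the small-cell rule. This reading is possible but weak: the same phrase is the prevalence denominator, where it must mean everyone, and section 9.7 uses the word for the two drug groups. At best the text leaves the result to the programmer.

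**New cases over all treated patients is a legitimate quantity.** It is, as the share of the whole cohort with a new-onset event. It is not what the population sentence describes, and the protocol does not present it as such.

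**The SAP can settle it.** Section 9.7 lets the SAP modify the protocol's plans. But the formula is fixed here, not left open. An amendment is promised only for major changes to primary endpoints, so a correction made in the SAP alone might leave the protocol wrong.

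**The consequence is limited.** This stands. Tolerability is Exploratory Objective 1, no formal comparison between groups is planned, prevalence for the same events has a sound denominator, and no primary objective depends on this formula.

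**Readings that go too far.** A reader might infer that every adverse-event incidence is understated. That fails for any event with no patient excluded, which could include events rarely seen before treatment. A reader might also infer that the intervals are always too narrow; the 80% example contradicts that. Finally, prevalence over the whole disease history is not the relevant quantity: only events in the 14-, 30- or 60-day washout count, so arguments from heavy pre-treatment do not give B/N directly.

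**Conclusion.** The inconsistency is real and visible within section 9.7.6. Read as written, the formula understates incidence by the relative amount B/N for each event with at least one patient excluded for an event in the washout, and the 95% CI is centred too low on the wrong n. Events with B = 0 are unaffected.

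The algebra rests on no assumption beyond reading the denominator literally. The percentages shown do: the at-risk incidences, the B/N values and the use of 133 as cohort size are illustrative, because the protocol gives no washout frequencies and no final cohort size. The documents therefore cannot say how large the bias will be for any named event.

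Severity: should-fix. It is a wrong estimator for a safety outcome in a study designated as a PASS, but the outcome is exploratory and descriptive, and the documents do not support ranking it as a threat to the study's primary objectives.

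**What to change.** In section 9.7.6:

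1. Replace the incidence denominator with the number of patients in the drug cohort without the event in the event-specific washout of Table 3.
2. Compute the 95% CI on that number and report it beside each incidence. Under the CMS rule in section 9.4, mask it where needed. Showing N and N − B together reveals B by subtraction, so B between 1 and 10 also needs care.
3. Tie both time references, the one in the population sentence and the one in the numerator, to the same Table 3 washout windows, so that one look-back defines who is excluded.
4. Check that every Table 3 event carries a washout footnote. In the text as read, the ICANS and hypophosphataemia rows show none. This may be a conversion loss, but the corrected denominator needs a window for each event.
5. Leave the prevalence formula unchanged.

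The cost is one formula, one clarified look-back and one extra column in the tables. No new data are needed. Reported incidences rise wherever x and B are both above zero, so any interim incidences already computed with the written formula should be recalculated before they are set beside the final ones.
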